2.2.3 Logistic Regression

For the univariate analyses, coefficients, Wald's chi-square p-values, odds ratios, and 95% confidence intervals for the odds ratios will be displayed. Note that for variables created from subsets of subjects, only variables with at least 10 subjects in the given subset will be included in this analysis.

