The GRASP registry was a single-center, prospective, observational study of consecutive high surgical risk patients with moderate-to-severe or severe MR undergoing percutaneous mitral valve repair with the MitraClip System at Ferrarotto Hospital (Catania, Italy). The study does not have specific exclusion criteria; and the indication for MitraClip therapy was established by a multidisciplinary Heart Team. The degree of preprocedural MR was quantified according to current guidelines by two expert echocardiographers. A total of 117 consecutive patients underwent MitraClip implantation between August 2008 and October 2012 as part of the GRASP registry³⁰. MR grade 3+ or 4+ was present in 98% of patients, and NYHA functional class symptoms in 80% of patients. Acute procedural success was achieved in all patients. MR was reduced to 1+ and 2+ post-procedure in 63% and 37% of patients, respectively. MAEs occurred in 4 patients (4.3%) at 30 days. One patient died from gastrointestinal bleeding within 30 days. Results from the GRASP registry further support the safety and efficacy of the MitraClip device in a real-world setting.

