Degenerative MR etiology was present in a majority (85.9%) of patients, whereas functional MR was noted in 17.5% (FMR only 8.6%; mixed etiology 8.9%). Ninety-three percent (93%) of patients presented with 3+ or 4+ MR at baseline. Significant left ventricular dilation (end-systolic dimension ≥ 40 mm) was present in 32.2%. The median LVEF was 55% and 35.4% of the patients had an LVEF $< 50\%$. Baseline mean mitral gradient was ≥ 5 mm Hg in 9.2%, and the MV area was < 4 cm² in 20.5%. Severe tricuspid regurgitation was present in 16.0% of the patients.

The MitraClip was predominantly implanted in the A2-P2 region (82.8% of cases). MR reduction to $\leq 2+$ was achieved in 93.0% of patients, while MR grade $\leq 1+$ was achieved in 61.8%. Single-leaflet device attachment occurred in 1.5% of treated patients. There were 4 reported cases of device embolization (0.1%). Major or life-threatening bleeding (VARC-2 criteria) occurred in 3.9%. The rates of stroke (0.4%) and myocardial infarction (0.1%) were both low. Twenty patients (0.7%) had in-hospital conversion to open cardiac surgery. Overall in-hospital mortality was 2.7%. The median length of hospital stay was 2 days and a majority (85.9%) of the treated patients were discharged directly home.

A total of 1,867 patients (63.2%) from 139 hospitals had records that could be linked to CMS administrative claims. Patients with linked CMS claims data tended to be older, had a lower rate of comorbidities such as diabetes and prior myocardial infarction, and were less likely to have functional MR. However; the STS-predicted risks of operative mortality for MV repair and MV replacement were higher in patients with linked CMS claims data compared to those without linked CMS claims data.

In this cohort, 30-day mortality, including in-hospital events, was 5.2% and the rate of re-hospitalization for heart failure was 4.9%. A majority (95.5%) of patients were discharged from hospital with MR $\leq 2+$, alive and free from MV surgery at 30 days.

One-year mortality in patients with linked CMS claims data was 25.8% and the rate of re-hospitalization for heart failure at 1 year was 20.2%. The combined endpoint of death or heart failure re-hospitalizations at 1 year occurred in 37.9% of the patients. These endpoints were lower for patients who had degenerative MR etiology (24.7%, 20.5%, and 35.7%, respectively) compared to those who had functional MR etiology (31.2%, 32.6%, and 49.0%, respectively).

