1.4 Endpoints

1.4.1 Safety and Performance Measures

• Safety

The assessment of safety will include all occurrences through 30 days post procedure.

Occurrence of Major Adverse Events (MAE) at 30 days

MAE is defined as a composite of all-cause Death, Myocardial Infarction, Stroke, or non-elective Cardiovascular (CV) surgery for device related complications (CEC adjudicated).

Performance

The assessment of performance measures will include all data reported at 30-day visits for this study. MR Reduction to \leq 2+ at 30 days

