2.4 Size Calculations

A sample size of 1000 subjects is expected to adequately capture data on a wide range of subjects with primary or secondary MR, subjects with or without complex valve anatomy, and subjects from Europe and the United States.

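### The logistic regression entry rule in SAP 2.2.3 counts subjects rather than events; at the 10-subject floor, low-rate outcomes such as 30-day death or MAE then usually give no finite Wald odds ratio

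*SAP*

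**What the plan says.** SAP 2.2.3 (Logistic Regression) states that for the univariate models "coefficients, Wald's chi-square p-values, odds ratios, and 95% confidence intervals for the odds ratios will be displayed". It then sets one entry condition: "only variables with at least 10 subjects in the given subset will be included in this analysis". The sentence opens by limiting that condition's scope: "Note that for variables created from subsets of subjects". The visible text contains no requirement on events or non-events, no exact or penalised alternative, and no instruction for a fit that does not converge.

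The section names neither the outcome nor the candidate predictors. SAP 1.4.1 offers two natural outcomes: the safety measure, "Occurrence of Major Adverse Events (MAE) at 30 days", and the performance measure, reduction of MR to 2+ or less at 30 days. The planned size is 1,000 (SAP 2.4: "A sample size of 1000 subjects is expected to adequately capture data on a wide range of subjects"). No event rate is assumed for this study; the Protocol gives only historical rates.

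SAP 2.7 describes the subgroup analyses as exploratory, SAP 2.2.1.2 allows p-values for generating hypotheses, and SAP 2.9 says that no hypotheses are tested.

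**The concern.** A logistic odds ratio for a binary predictor is finite only if each level of the predictor contains both events and non-events. The number of subjects in a level does not guarantee this. A rule based on 10 subjects can therefore admit a predictor whose odds ratio cannot be estimated. When the outcome is rare, the predictors that can be estimated are those whose small category happened to contain an event, and that selection pushes their odds ratios upward.

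At stake is how a table of univariate predictors would read. An uncommon feature could appear either with an odds ratio near 0 and a p-value near 1, or with an odds ratio of 2 or more, when the data support neither. The Protocol (1.0) intends to look for patient or valve features that suit these devices, and SAP 2.7 ties exploratory results to publication and presentation.

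**Working it through.** The plan gives no derivation for the threshold of 10, so there is no figure to reproduce. The check asks what the rule does at its floor.

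**Inputs and reading.** The floor is read as 10 subjects in one category of a binary predictor, against 1,000 − 10 = 990 others. The outcome is an assumption, so a range of rates from the Protocol is used. Two sources for the low end are "MAEs occurred in 4 patients (4.3%) at 30 days" (Appendix I, 2.1) and "30-day mortality, including in-hospital events, was 5.2" per cent (Appendix IV, US registry).

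**Step 1: chance of zero events in 10 subjects, (1 − p)^10.**

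| Outcome and source | p | Zero events |
|---|---|---|
| 30-day MAE, single-centre registry (App. I, 2.1) | 4.3% | 0.957^10 = 64% |
| 30-day death, German registry (App. IV) | 4.5% | 63% |
| 30-day death, US registry (App. IV) | 5.2% | 0.948^10 = 59% |
| MR not reduced to 2+ at 30 days, continued-access non-high-risk arm (App. IV; 100 − 89) | 11% | 0.89^10 = 31% |
| 30-day MAE on a broader definition, same arm | 11.4% | 30% |
| 1-year death, European pilot registry (App. IV) | 15.3% | 19% |
| 1-year death, German registry (App. IV) | 20.3% | 10% |
| 1-year death, US registry, linked claims (App. IV) | 25.8% | 5% |

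The 4.3% is used as printed; 4/117 would be 3.4%, which gives about 71%. Zero events is the majority result only when (1 − p)^10 > 0.5, that is, p < 1 − 0.5^(1/10) = 6.7%.

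**Step 2: what the model returns.** Take 51 events in the 990 others (5.2%, rounded), leaving 939 non-events.
- 0 of 10: no finite estimate. A standard maximum-likelihood fit stopped at 25 iterations gave coefficient −16.5, SE 5087, p = 0.997.
- 1 of 10: (1 × 939)/(9 × 51) = 2.05 (95% CI 0.25 to 16.5).
- 2 of 10: (2 × 939)/(8 × 51) = 4.60 (0.95 to 22.2).
- 3 of 10: (3 × 939)/(7 × 51) = 7.89 (1.98 to 31.4).

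At this background rate the smallest finite odds ratio above zero is therefore already about 2.

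**Step 3: no true effect, 10 versus 990 subjects, 400,000 simulated tables per rate.**

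| Rate | Not estimable | Median finite OR | Finite ORs above 1.5 | Wald p < 0.05 among finite fits |
|---|---|---|---|---|
| 4.3% | 64% | 2.57 | over 99% | 16% |
| 5.2% | 59% | 2.13 | 99% | 9% |
| 7% | 48% | 1.58 | 62% | 6% |
| 10% | 35% | 1.11 | 41% | 6% |
| 20.3% | 10% | 1.01 | 35% | 4% |

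If non-estimable fits are counted as non-significant, the proportion with p < 0.05 is 5.6% at a 4.3% rate and 3.9% at 5.2%. The distortion thus lies in which odds ratios get reported and how large they are. The overall rate of false signals is close to nominal.

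**Step 4: subjects needed.** Five expected events need 5/p subjects: 117 at 4.3%, 97 at 5.2%, 46 at 11% and 25 at 20.3%. To keep the zero-event chance below 5% takes 69, 57, 26 and 14 subjects at the same rates.

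**The case against.** A reader might infer that predictors admitted by this rule usually have no events and that their odds ratios are biased upward in general. The documents do not support that reading, for four reasons.

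- **Outcome.** SAP 2.2.3 names none. For MR not reduced to 2+ at 30 days (11%) or 1-year death (15% to 26%), the zero-event chance is 5% to 31%, and by 10% to 20% the median finite odds ratio is 1.1 to 1.0. What remains there is low precision, which the planned 95% intervals would show.
- **Scope.** The rule covers only subset-derived variables, and the figures describe a predictor exactly at the floor. The wording could also mean 10 subjects in whom the variable was recorded. In that case the zero-event chance is the same, but precision is worse.
- **Purpose.** Nothing in 2.2.3 links the regression to the anatomical aim. The anatomical comparison that is spelled out (Protocol 5.1.1) splits all subjects into two groups, and nothing suggests that either would be near 10.
- **Possible removals.** SAP 2.2.3 opens abruptly, and the population and subgroup text is blank in the public version. Outcomes or sparse-data handling may have stood there, so the missing outcome is not counted as an error.

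In addition, no success criterion in the SAP rests on these odds ratios, SAP 2.2.1.2 already plans counts and exact intervals for binary variables, and a standard error of 5087 is hard to miss.

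All of this narrows the point. What stands is that the rule as printed counts the wrong quantity. The higher historical MAE rates are also a weak guide to this study. Its MAE is limited to death, MI, stroke and non-elective surgery for device-related complications. The pivotal randomised trial's broader composite gave 7.9%, and 4.5% once bleeding was left out (Appendix IV).

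**Conclusion.** The concern holds for low-rate outcomes at the 10-subject floor. With 30-day death or MAE at 4.3% to 5.2%, 59% to 64% of such fits have no finite odds ratio. Under no true effect the rest centre on 2.1 to 2.6 instead of 1. Above about 6.7%, zero events is no longer the majority result. By 10% to 20% the bias has largely gone, and the remaining fault is that 10 subjects carry too little information.

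This rests on three assumptions: the outcome is one of the study's 30-day or 1-year endpoints, historical rates carry over, and the threshold refers to 10 subjects in a category against about 990 others. An unconditional claim about all admitted predictors or all outcomes would go beyond the documents. The effect is confined to exploratory results, but those are intended for publication and the rule is easily corrected.

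**What to change.** Replace the 10-subject rule with one based on events and non-events in each predictor level. For example, report the ordinary odds ratio with Wald interval and p-value only when every predictor-by-outcome cell holds at least 5 subjects. Five is a conventional choice with no source in the documents. Where the condition fails, report Firth penalised logistic regression with a profile-likelihood 95% interval. Print events over subjects for each level in both cases. State whether the rule applies to categories of a predictor or to variables recorded in only part of the cohort.

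In a two-by-two table the Firth estimate equals adding 0.5 to each cell. For 0 of 10 against 51 of 990 it is (0.5 × 939.5)/(10.5 × 51.5) = 0.87 (0.05 to 15.0). For 1 of 10 it is (1.5 × 939.5)/(9.5 × 51.5) = 2.88 (0.50 to 16.5). These intervals are Wald intervals on the adjusted counts, so profile-likelihood limits will differ somewhat. The estimates are finite and plainly uninformative, which is the correct message from 10 subjects.

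The cost is a change of SAP wording and one software option, with no effect on data collection or sample size. The downside is that fewer predictors receive an ordinary Wald odds ratio, and Firth intervals for rare features will be wide.

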2.3 Endpoints Analyses

Study endpoints defined in section 1.4 will be summarized descriptively using methods described in Section 2.2.Sample

2.4 Size Calculations

A sample size of 1000 subjects is expected to adequately capture data on a wide range of subjects with primary or secondary MR, subjects with or without complex valve anatomy, and subjects from Europe and the United States.

2.5 Interim Analysis

No formal interim analyses are planned for this study. As such, no formal statistical rule for early termination of the trial is defined. Descriptive analysis based on accumulated data may be produced for publication and presentation purposes.

2.6 Timing of Analysis

The analysis will be performed after database lock per analysis population who complete their 1-year follow-up visits or terminated from study before their 1-year follow-up visits.

2.7 Subgroups for Analysis

The following subgroup analyses are to provide understanding and evaluation of the safety and performance of MitraClip treatment in a various patient populations, for exploratory purpose and the supports of publication and presentation.

2.8 Handling of Missing Data

All analyses will be based on available data. Missing data will not be imputed. Any unused or spurious data will be documented as appropriate in the clinical report. For APS endpoint, a 30-day echocardiogram will be used if discharge is unavailable or uninterpretable.

2.9 Multiplicity Issues

There are no multiplicity issues since we did not have hypothesis testing.

3.0 DESCRIPTIVE ENDPOINTS AND ADDITIONAL DATA

The following analyses will be conducted based on analysis population define in 2.1.1

3.1 Baseline and Demographic Characteristics

The following baseline and demographic variables will be summarized: gender, age, height, weight, baseline risk factors, medical history, echocardiogram, implant procedural characteristics, device usage, quality of life and functional status, etc.

3.2 Adverse Events

All of the adverse events (AEs), serious adverse events (SAEs), adverse device effects (ADEs) and serious adverse device effects (SADEs) will be summarized using number of events, the percentage of subjects with events, and event rates per MedDRA coding.

All CEC adjudicated adverse events up to 30 days post index procedure will also be summarized using number of events, the percentage of subjects with events, and event rates.

3.3 Subject Early Termination

Subject early termination reasons including deaths, withdrawals, lost-to-follow-up, etc. will be summarized at all scheduled visits.

3.4 **Protocol Deviation**

Protocol deviations will be summarized by category for subjects in whom a protocol deviation was reported. Number of protocol deviations and number of subjects with deviation will be summarized by deviation categories.

3.5 Descriptive Endpoints or Additional Data

COVID-19 assessment will be listed.

4.0 **DOCUMENTATION AND OHER CONSIDERATIONS**

All analyses will be performed using SAS® for Windows, version 9.3 or higher.

